7.7 EXTENT OF EXPOSURE

A descriptive statistics table with mean, SD, Q1, median, Q3 and range of the number of days a patient was on-treatment will be provided for the TS. The tables will also provide the sum total of the time (in years) that all patients were on-treatment.

A separate listing will be created of any patients that switched treatment at any time indicating exposure to each treatment.

A frequency table of number and percent of patients belonging to each categorical range of exposure weeks will be provided as well. The following are the categories of exposure-ranges (in weeks):

>0 to 8 weeks, >8 to 15 weeks, >15 to 21 weeks, >21 to 26 weeks, >26 weeks

7.8 SAFETY ANALYSIS

All safety analyses will be performed on the TS.

7.8.1 Adverse events

AEs will be coded using the latest version of the MedDRA coding dictionary at database lock.

Any clinically significant new finding in the physical examination, vital signs (BP and pulse symptoms) and in the 12-lead ECG starting after visit 2 (randomisation visit) will be considered as an AE and will be reported as such.

The analyses of AEs will be descriptive in nature. All analyses of AEs will be based on the number of patients with AEs (not the number of AEs). For this purpose, AE data will be combined in a 2-step procedure into AE records.

In a first step, AE occurrences, i.e. AE entries on the CRF, will be collapsed into AE episodes provided that all of the following applies:

- The same MedDRA lowest level term was reported for the occurrences.
- The occurrences were time-overlapping or time-adjacent (time-adjacency of 2 occurrences is given if the second occurrence started on the same day or on the day after the end of the first occurrence. Exceptions: [1] Hypoglycaemic events are only collapsed if they occur within 12 hours of each other. The 12 hour period will begin with the first hypoglycaemia onset time. If another event occurs outside this initial 12 hour window a new period for collapsing will begin. [2] GI events will not be collapsed if they are representative of different types (i.e. fungal balanitis or vulvovaginitis versus other than fungal balanitis or vulvovaginitis). [3] Sepsis events will not be collapsed if they are representative of different sources of infection (i.e. urinary tract [urosepsis] versus other than urinary tract)
- Treatment did not change between the onset of the occurrences OR treatment changed between the onset of the occurrences, but no deterioration was observed for the later occurrence.

In a second step, AE episodes will be condensed into AE records provided that the episodes were reported with the same term on the respective MedDRA level and that the episodes are

assigned to the same treatment. For further details on summarization of AE data, please refer to the guideline 'Handling and summarization of adverse event data for clinical trial reports and integrated summaries' ([6](#)).

7.8.1.1 Assignment of AEs to treatment

The analysis of AEs will be based on the concept of treatment-emergent AEs. This means that all AEs occurring between first drug intake until 7 days after last drug intake will be assigned to the first treatment received. All AEs occurring before first drug intake will be assigned to 'pre-treatment' and all AEs occurring after last drug intake + 7 days will be assigned to 'post-treatment'.

In general, in-text AE tables will only present AEs assigned to the first treatment taken, except drug-related AEs, which will be presented as actual treatment taken at each given timepoint. End-of-text tables will display, in addition, AEs observed 'pre-treatment' (including AEs observed during screening and placebo run-in regardless of treatment group). Appendix 16.1.9.2 will include an analysis where AEs and serious AEs (SAEs) are assigned to the following phases: Screening, placebo run-in, each treatment group, post-treatment for each treatment group.

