7.3.3 Safety analyses

Adverse events will be coded using the Medical Dictionary for Regulatory Activities (MedDRA) coding dictionary. Standard BI summary tables and listings will be produced. All adverse events with an onset between start of treatment and end of the residual effect period (REP), a period of ≤ 7 days after the last dose of trial medication, will be assigned to the treatment period for evaluation.

All treated patients will be included in the safety analysis. In general, safety analyses will be descriptive in nature and will be based on BI standards. No hypothesis testing is planned. Statistical analysis and reporting of adverse events will concentrate on treatment-emergent adverse events. To this end, all adverse events occurring between start of treatment and end of the REP will be considered 'treatment-emergent'. The REP is defined as ≤ 7 days following last intake of trial medication. Adverse events that start before first drug intake and deteriorate under treatment will also be considered as 'treatment-emergent'. Frequency, severity, and causal relationship of adverse events will be tabulated by system organ class and preferred term after coding according to the current version of the MedDRA.

Laboratory data will be analysed both quantitatively as well as qualitatively. The latter will be done via comparison of laboratory data to their reference ranges. Values outside the reference range as well as values defined as clinically relevant will be highlighted in the listings. Treatment groups will be compared descriptively with regard to distribution parameters as well as with regard to frequency and percentage of patients with abnormal values or clinically relevant abnormal values. Vital signs, physical examinations, or other safety-relevant data observed at screening, baseline, during the course of the trial and at the end-of-trial evaluation will be assessed with regard to possible changes compared to findings before start of treatment.

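### SAP 7.8.1.1 assigns every AE with onset before first drug intake to pre-treatment, whereas protocol 7.3.3 counts those that worsen on treatment as treatment-emergent

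*SAP*

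**What the plan says.** **Protocol 7.3.3 (Safety analyses)** gives two routes to treatment-emergent status. The first is onset between start of treatment and the end of the residual effect period: "The REP is defined as ≤ 7 days following last intake of trial medication". The second covers earlier onsets: "Adverse events that start before first drug intake and deteriorate under treatment will also be considered as" treatment-emergent.

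**SAP 7.8.1.1 (Assignment of AEs to treatment)** names the same concept and then spells it out by timing alone: "all AEs occurring between first drug intake until 7 days after last drug intake will be assigned to the first treatment received". For everything earlier, "All AEs occurring before first drug intake will be assigned to" the pre-treatment category. On presentation, "in-text AE tables will only present AEs assigned to the first treatment taken", apart from drug-related AEs, which go by actual treatment. Pre-treatment AEs are added in the end-of-text tables, not split by arm, and an appendix shows AEs by study phase.

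**SAP 7.8.1 (Adverse events)** decides when several CRF entries are merged into one episode. Entries that straddle a treatment change are merged only where "treatment changed between the onset of the occurrences, but no deterioration was observed for the later occurrence".

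**SAP 3 (Introduction)** says the plan rests on Section 7 of the protocol. The visible part of SAP 4, which lists changes to the planned analysis, says nothing about the treatment-emergent definition.

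**The concern.** The two documents define one concept in two ways. The 7-day window after last intake is the same in both, so the whole difference is the missing deterioration clause. The SAP does not merely stay silent on it: its pre-treatment sentence covers all earlier onsets and so excludes the events that the protocol includes.

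This could matter in practice. Protocol 5.2.2.2 collects AEs from informed consent, and the Flow Chart places screening at Day -21, about three weeks before the first randomised dose. Some AEs may therefore be open at that dose. If one of them becomes more severe or serious on study drug, or leads to its discontinuation, the protocol would show it in the comparison of empagliflozin with placebo. The SAP rule, read literally, could leave it out.

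**Working it through.** No sample size, rate or test statistic is involved, so the check applies both rules to each way such an event can be recorded. It assumes that the move from screening or run-in to randomised drug counts as a treatment change under SAP 7.8.1. That fits SAP 6.1, which lists these as separate intervals.

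| AE with onset before first intake | SAP 7.8.1 and 7.8.1.1 | Protocol 7.3.3 | Agree? |
|---|---|---|---|
| Does not worsen, one entry | Pre-treatment | Not treatment-emergent | Yes |
| Second entry after first dose, no worsening | Merged if same lowest level term and adjacent or overlapping in time; the episode began before first dose, so pre-treatment | Not treatment-emergent | Yes |
| Worsening entered as a second entry after first dose | Not merged; the later entry has its own on-treatment onset and is assigned to treatment | Treatment-emergent | Yes |
| Worsening recorded by updating the existing entry | One onset, before first dose; the merging rule has nothing to act on; pre-treatment | Treatment-emergent | **No** |

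Only the last row conflicts. Three further checks define what is lost there.

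1. **Does the exception for drug-related AEs rescue the event?** No. SAP 6.1 ties actual medication to the time of AE onset, which here precedes randomised drug.
2. **Does the event disappear from the report?** No. It remains in the end-of-text tables and the appendix as pre-treatment. It leaves the in-text tables that compare the arms.
3. **Which AEs of special interest are exposed?** Hepatic injury is defined by laboratory changes after randomisation, and decreased renal function by at least a doubling of creatinine from baseline (protocol 5.2.2.1, SAP 7.8.1.5). Those criteria are met only after baseline, so these two are largely outside the problem. Categories identified as ordinary events, such as urinary tract infection, genital infection and volume depletion, follow the general rule and could be touched.

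On size, a count would need the share of patients with an AE open at first dose, the share of those that worsen, and the share of worsenings kept inside one entry. The documents give none of these. What can be stated is the weight of a single case: one patient in a planned arm of 77 is 1/77 = 1.3 percentage points.

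**The case against.** The strongest reply is that the SAP already deals with deterioration. The merging rule in 7.8.1 comes just before the disputed section and looks like the working form of the protocol clause. Protocol 5.2.2.2 also asks sites to record worsening of the underlying disease or of other pre-existing conditions as an (S)AE, which leans towards a new entry. If sites always do that, nothing is lost. CRF completion instructions and the company AE guideline cited in SAP 7.8.1 may settle the matter, and neither is available here.

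Much of this stands. A reader might infer that every run-in event that worsens on drug drops out of the main safety tables; the merging rule shows that this is not so. What remains is that the protocol instruction does not clearly reach an AE already open on the CRF since consent, and that the merging rule cannot act on a single entry.

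One could also say that the SAP assumes familiarity with the protocol and simply restated its definition incompletely. That may be how it arose, but a programmer following an unqualified instruction for all earlier onsets will not apply an exception found elsewhere. Nor does a looser reading of occurring, to include AEs still ongoing at first dose, repair it: the same event would then meet both SAP sentences, and ongoing AEs that never worsened would count as well.

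**Conclusion.** SAP 7.8.1.1 is wrong as written, because it contradicts protocol 7.3.3 and no visible text declares a change. Part of SAP 4 is not shown, so that last statement rests on visible text only. Severity is low. The loss is confined to worsening recorded within one existing entry, affects the in-text tables only, and concerns descriptive safety summaries with no hypothesis test. The number affected cannot be estimated and may be zero.

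Two stronger readings are not supported. A reader might infer that the rule conceals harm from empagliflozin. The rule is the same for both arms, placebo patients can also worsen, and the documents do not show which arm would lose more events. A reader might also infer that the special-interest tables as a whole are compromised; the laboratory-defined hepatic and renal categories are largely not exposed.

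**What to change.** Make three changes in SAP 7.8.1.1:

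- Limit the pre-treatment sentence to AEs with onset before first intake that do not deteriorate under treatment.
- Restore the protocol 7.3.3 clause. Assign deteriorated events to the first treatment received, in line with the SAP's existing convention, and drug-related AEs to the actual treatment at deterioration.
- State that on-treatment worsening of an open AE is captured as a new occurrence with its own onset date. The AE items that protocol 5.2.2.2 gives as examples include onset, end date, intensity and seriousness but no date of worsening, so without this the clause may not be programmable for single entries. With it, the onset-based wording on actual medication in SAP 6.1 also works unchanged.

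The cost is a few sentences of SAP text before unblinding, plus a matching line in the CRF instructions if they do not already say this. Where sites already open a new entry, no table changes. Otherwise a blinded listing of AEs that start before and end after first intake, or are still ongoing, would show which entries need a query to the site.

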7.8.1.2 Analysis of other significant AEs

Other significant AEs will be reported and summarised according to ICH E3 criterion ([7](#)). Thus, AEs classified as 'other significant' will include those non-serious and non-significant AEs with:

- 'action taken = discontinuation' or 'action taken = reduced', or
- marked haematological and other lab abnormalities or lead to significant CT as identified by the Clinical Monitor/Investigator at a Medical Quality Review meeting (MQRM) or BRPM.

7.8.1.3 AE summaries

An overall summary of AEs will be presented.

The frequency of patients with AEs will be summarised by treatment, primary SOC and PT. AEs will also be reported by intensity. Separate tables will be provided for patients with other significant AEs, for patients with AESI, for patients with SAEs, for patients with AEs leading to discontinuation, and for patients with drug-related AEs.

The SOC's will be sorted according to the standard sort order specified by European medicines agency (EMA), PTs will be sorted by frequency (within SOC).

7.8.1.4 Analysis of hypoglycaemic events

The investigator will record for each AE whether it represents a hypoglycaemic AE and, if so, record additional information to assess the intensity of the hypoglycaemic AE. On the basis of this information the hypoglycaemic AE will be classified as:

- asymptomatic hypoglycaemia: event not accompanied by typical symptoms of hypoglycaemia but with a measured plasma glucose concentration < 3.0 mmol/L (< 54 mg/dL),
- documented symptomatic hypoglycaemia with a measured plasma glucose concentration ≥ 3.0 mmol/L and ≤ 3.9 mmol/L (≥ 54 mg/dL and ≤ 70 mg/dL): event accompanied by typical symptoms of hypoglycaemia,
- documented symptomatic hypoglycaemia with a measured plasma glucose concentration < 3.0 mmol/L (< 54 mg/dL): event accompanied by typical symptoms of hypoglycaemia but no need for external assistance,
- severe hypoglycaemic episode: event requiring the assistance of another person to actively administer carbohydrate, glucagon or other resuscitative actions.
- symptomatic hypoglycaemia and plasma glucose concentration > 3.9 mmol/L (> 70 mg/dL)
- symptomatic hypoglycaemia and plasma glucose concentration not measured

Asymptomatic hypoglycaemia with a measured plasma glucose concentration ≥ 3.0 mmol/L and ≤ 3.9 mmol/L (≥ 54 mg/dL and ≤ 70 mg/dL) will also be recorded by the investigator but will not be regarded as an AE.

The number of patients with hypoglycaemic AEs or non-AEs according to investigator's judgement will be tabulated by treatment group. A subgroup analysis of confirmed hypoglycaemic AEs with respect to age category, antidiabetic rescue therapy and renal function will be performed. Confirmed hypoglycaemic AEs are defined as hypoglycaemic AEs according to investigator's judgement confirmed with plasma glucose concentration ≤ 3.9 mmol/L (≤ 70 mg/dL) or required assistance.

The impact of treatment on the occurrence of hypoglycaemic AEs will be explored using logistic regression with model involving treatment, renal function, pretreatment with metformin and continuous baseline HbA_{1c}. Time to the onset of the first hypoglycaemic AE will be analysed by Kaplan-Meier estimates. The logistic regression and Kaplan-Meier analysis will be performed on confirmed hypoglycaemic AEs.

Summaries of hypoglycaemic events will include total number of hypoglycaemic events, descriptive hypoglycaemic event rate, number of episodes per patient, severity and intensity of the worst episode, action taken, minimum glucose level of worst episode, and time to onset of first episode. Hypoglycaemic events will also be summarised by baseline eGFR category (CKD-EPI) and age group.

In addition, the frequency of hypoglycaemic AEs characterized by the latest BICMQ version terms will also be produced.

Different tables will be shown for (i) patients with investigator defined asymptomatic or symptomatic hypoglycaemia reported as AE or non-AE, (ii) patients with confirmed hypoglycaemic AEs, i.e. hypoglycaemic AEs that had a plasma glucose concentration ≤ 3.9 mmol/L (≤ 70 mg/dL) or required assistance, and, (iii) patients with minor, confirmed hypoglycaemic AEs, defined as a hypoglycaemic event that had a plasma glucose concentration ≤ 3.9 mmol/L (≤ 70 mg/dL) but did not require assistance.

7.8.1.5 AEs of special interest (AESI)

The protocol defines the following AEs that for analysis purposes will be considered as AESIs:

- Decreased renal function: creatinine shows a ≥ 2 fold increase from pre-treatment/baseline and is above the upper limit of normal (ULN)
- Hepatic injury defined by the following alterations of liver parameters after randomization: AST and/or ALT ≥ 3 fold ULN and bilirubin ≥ 2 x ULN measured in the same blood sample, or isolated elevation of AST and /or ALT ≥ 5 fold ULN irrespective of any bilirubin elevation.
- Metabolic acidosis, ketoacidosis and diabetic ketoacidosis (DKA)

Events of these AESIs are identified through the AE being flagged by the investigator as significant on the case report form (CRF).

AE frequency tables will also be created for renal and hepatic events based on narrow SMQs.

Renal:

- Acute renal failure: 20000003 (narrow SMQ)

Hepatic:

- Liver related investigations, signs and symptoms: 20000008 (narrow SMQ)
- Cholestasis and jaundice of hepatic origin: 20000009 (narrow SMQ)
- Hepatitis, non-infectious: 20000010 (narrow SMQ)
- Hepatic failure, fibrosis and cirrhosis and other liver damage-related conditions: 20000013 (narrow SMQ)

AE frequency tables will be created for the following AESI events based on narrow SMQs:

- Malignancies: (20000090) (narrow SMQ)

The following additional AESI will also be assessed and AE frequency tables constructed based on the latest MedDRA version at database lock:

- GI (BICMQ genital tract infections EMPA folder, investigator assessment)
- UTI (narrow BICMQ, investigator assessment)

AESIs of UTIs and GIs will additionally be summarised by age group, baseline HbA1c, intensity (mild, moderate or severe), whether leading to discontinuation of treatment, time of occurrence (in the first 3 months of treatment or after), duration (<7 days, 7-14 days and >14 days), sex, by how the event was treated (no treatment, therapy assigned, hospitalisation) and the number of episodes per patient.

The following AESIs based on investigator assessment will also be tabulated by treatment group:

- Acute pyelonephritis: patient incidence overall and by intensity, and treatment required (0, 1, 2, >2 antimicrobials)

- Sepsis: patient incidence overall and by source of infection
- Asymptomatic bacteriuria: patient incidence overall
- Bone fractures: patient incidence overall and by type of fracture, intensity, and time to onset of first fracture

In the number of episodes analysis of UTI and GI AEs will be collapsed within each special search category (SSC) regardless of PT with the collapsing following the description at the start of [Section 7.8.1](#) but the condensing will not be conducted in order to maintain multiple episodes per patient.

Kaplan-Meier time to event analyses will also be presented for the UTI and GI AESIs. These analyses will also be presented by sex.

An additional AESI of volume depletion will be used and an AE frequency table constructed. The AESI will be based on the latest MedDRA version at database lock:

- Volume depletion: BICMQ (EMPA folder/sub-BICMQ origin vascular narrow)

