[figure not shown]
[figure not shown]
[figure not shown]
[figure not shown]

Clinical Trial Protocol

Doc. No.: c01945509-06

BI Trial No.:	1245.29
BI Investigational Product:	Empagliflozin
Title:	A randomised, double-blind, placebo-controlled, parallel group, efficacy and safety study of empagliflozin (10 mg, 25 mg) administered orally, once daily over 24 weeks in hypertensive black/African American patients with type 2 diabetes mellitus
Clinical Phase:	IIIb
Trial Clinical Monitor:	 Tel:  Fax: 
Co-ordinating Investigator:	 Phone:  Fax: 
Status:	Final Revised Protocol (based on global amendment 4)
Version and Date:	Version: 5.0 Date: 18 July 2016
Page 1 of 144	
Proprietary confidential information. © 2016 Boehringer Ingelheim International GmbH or one or more of its affiliated companies. All rights reserved. This document may not - in full or in part - be passed on, reproduced, published or otherwise used without prior written permission.	

CLINICAL TRIAL PROTOCOL SYNOPSIS

Name of company: Boehringer Ingelheim		Tabulated Trial Protocol	
Name of finished product: NA			
Name of active ingredient: Empagliflozin			
Protocol date: 15Apr2014	Trial number: 1245.29		Revision date: 18 July 2016
Title of trial:	A randomised, double-blind, placebo-controlled, parallel group, efficacy and safety study of empagliflozin (10 mg, 25 mg) administered orally, once daily over 24 weeks in hypertensive black/African American patients with type 2 diabetes mellitus		
Co-ordinating Investigator:			
Trial sites	Multi-centre trial		
Clinical phase:	IIIb		
Objectives:	The objective of the current study is to investigate the efficacy and safety of empagliflozin (10 mg or 25 mg) compared to placebo on glucose control over 24 weeks in hypertensive black/African American patients with Type 2 Diabetes Mellitus (T2DM). A second objective of the study is to investigate the efficacy and safety of empagliflozin (10 mg or 25 mg) compared to placebo on BP over 12 weeks and on weight at 24 weeks in the same patient population. The study is designed to show superiority of empagliflozin over placebo.		
Methodology:	Randomised, double-blind, placebo-controlled, parallel group comparison		
No. of patients:	
total entered: 154 randomised hypertensive black/African American patients with type 2 diabetes mellitus (T2DM)
 
each treatment: 77 patients on empagliflozin 10 mg/25 mg 77 patients on placebo
		
Diagnosis :	T2DM and hypertension		

Proprietary confidential information.

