© 2016 Boehringer Ingelheim International GmbH or one or more of its affiliated companies. All rights reserved.

This document may not - in full or in part - be passed on, reproduced, published or otherwise used without prior written permission.

Patients showing these lab abnormalities need to be followed up according to [Appendix 10.4.2](#) of this CTP and the “DILI checklist” provided in RDC/ISF

- Decreased renal function: creatinine value shows a ≥ 2 fold increase from baseline and is above the upper limit of normal (ULN)
- Metabolic acidosis, ketoacidosis and diabetic ketoacidosis (DKA)

In case of metabolic acidosis, ketoacidosis and DKA further investigations should be done according to the medical judgment and the clinical course until a diagnosis is made and/or the patient is recovered.

DKA is defined by the diagnostic criteria in Table 5.2.2.1: 1 below, and as defined by the American Diabetes Association (ADA) ([R14-5435](#)).

Investigators should note that not all criteria in the table below need to apply for the diagnosis of DKA, and clinical judgment should also be taken into consideration. Due to its mechanism of action, empagliflozin may potentially modify the clinical presentation of DKA which may occur at lower plasma glucose levels than stated in Table 5.2.2.1: 1 below (see [Section 2.3](#) for further details).

In case of a suspected DKA the Investigator should ensure that appropriate tests are performed locally at the earliest opportunity according to local guidelines, such as a blood gas test (pH, bicarbonate) and that the patient is appropriately treated (i.e. hospitalized or referred to emergency treatment) according to local treatment guidelines.

Table 5.2.2.1: 1 Diagnostic criteria for DKA

	DKA		
	Mild	Moderate	Severe
Plasma Glucose (mg/dl)	>250	>250	>250
Arterial pH	7.25-7.30	7.00-7.24	<7.00
Serum bicarbonate (mEq/L)	15-18	10-<15	<10
Urine ketones*	Positive	Positive	Positive
Serum ketones*	Positive	Positive	Positive
Effective serum osmolality (mOsm/kg)**	Variable	Variable	Variable
Anion gap***	>10	>12	>12
Alteration in sensoria or mental obtundation	Alert	Alert/drowsy	Stupor/coma

* Nitroprusside reaction method

** Calculation: $2[\text{measured Na (mEq/L)} + \text{glucose (mg/dl)}]/18$

*** Calculation: $(\text{Na}^+) - (\text{Cl}^- + \text{HCO}_3^-)$ (mEq/L)

Proprietary confidential information.

© 2016 Boehringer Ingelheim International GmbH or one or more of its affiliated companies. All rights reserved.

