	Mild	Moderate	Severe																																						
Plasma Glucose (mg/dl)	>250	>250	>250																																						
Arterial pH	7.25-7.30	7.00-7.24	<7.00																																						
Serum bicarbonate (mEq/L)	15-18	10-<15	<10																																						
Urine ketones*	Positive	Positive	Positive																																						
Serum ketones*	Positive	Positive	Positive																																						
Effective serum osmolality (mOsm/kg)**	Variable	Variable	Variable																																						
Anion gap***	>10	>12	>12																																						
Alteration in sensoria or mental obtundation	Alert	Alert/drowsy	Stupor/coma																																						
Rationale for change		1) Update based on new template 2) Inclusion of DKA as AESI																																							
Section to be changed	19	5.2.3 Assessment of safety laboratory parameters																																							
Description of change		1) For the first visit after randomisation (4 weeks), only fasting plasma glucose and lipid status will be determined (see Flow Chart). 2) NAFLD fibrosis score will be calculated in-house at the central labs based on the following formula:																																							
Rationale for change		1) Lipids will not be assessed at this visit, correction 2) Clarification on where scores will be calculated																																							
Section to be changed	20	[REDACTED]																																							

Proprietary confidential information.

© 2016 Boehringer Ingelheim International GmbH or one or more of its affiliated companies. All rights reserved.

This document may not - in full or in part - be passed on, reproduced, published or otherwise used without prior written permission.

Number of global amendment		2.0
Section to be changed	21	6.2.1 Screening and run-in period (Visit 2.2); 6.2.2 Treatment period (Visit 5.1 and 7.1)
Description of change		
 1. Added, “If an invalid reading occurs for the Conclusion of Test reading, continue to trigger a manual reading until a valid reading is registered.” 2. (Visit 2.2 only) added word to, “Patients having two technically unsuccessful baseline ABPM/PWA sessions should not be randomized and must be discontinued.” 3. Updated and added language to allow for procedures for next visits to be done on the same day as the return ABPM session if the ABPM reading is successful.

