7.8.1.12 Adjudicated DKA Events

The assessments will be analysed on project level.

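### Ketoacidosis became an AESI only in Amendment 2, after recruitment had started, and the visible SAP text finds it by the investigator's flag alone, without a term search

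*SAP*

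**What the plan says.** Protocol 5.2.2.1 names three AESI groups: hepatic injury, decreased renal function, and "Metabolic acidosis, ketoacidosis and diabetic ketoacidosis (DKA". The log of Global Amendment 2 (Protocol 11.2, dated 12 August 2015) shows when the third group was introduced and gives the reason as "Inclusion of DKA as AESI".

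SAP 7.8.1.5 repeats the three groups and sets one rule for all of them: "Events of these AESIs are identified through the AE being flagged by the investigator as significant on the case report form (CRF". It then adds: "AE frequency tables will also be created for renal and hepatic events based on narrow SMQs". AESIs that the SAP itself introduces are also searched by term, for example "Volume depletion: BICMQ (EMPA folder/sub-BICMQ origin vascular narrow".

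For DKA, SAP 7.8.1.6 refers to 7.8.1.12, which says: "The assessments will be analysed on project level". All safety analyses use the treated set (SAP 7.8), and percentages are based on every patient in the set (SAP 7).

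**The concern.** A flag can record only what investigators have been asked to flag. Under the protocol versions before Amendment 2, ketoacidosis was not on the AESI list. An AE of this kind from that period would enter the flag-based AESI count only if someone went back and flagged it.

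A term search over coded AEs does not have this weakness, since it works the same way whatever version the patient was treated under. The SAP uses such searches for most of its other AESIs.

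At stake is the meaning of the ketoacidosis line in the AESI summary. Protocol 2.3 singles out DKA for special monitoring. It warns that presentation may be atypical, and Protocol 5.2.2.1 leaves room for clinical judgement in the diagnosis, so reported terms may vary. With the flag alone, a reader seeing zero could not tell no events from no flagged events.

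**Working it through.** No power, alpha or sample-size figure is involved. The check compares the identification rules and then looks at the timing.

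**1. How each AESI group is found (SAP 7.8.1.5, visible text)**

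| Event group | Investigator route | Term search |
|---|---|---|
| Decreased renal function | CRF flag | one narrow SMQ |
| Hepatic injury | CRF flag | four narrow SMQs |
| Metabolic acidosis / ketoacidosis / DKA | CRF flag | none named |
| Malignancies | none named | narrow SMQ |
| Genital infection | investigator assessment | BICMQ |
| Urinary tract infection | investigator assessment | narrow BICMQ |
| Volume depletion | none named | BICMQ |
| Acute pyelonephritis, sepsis, asymptomatic bacteriuria, bone fractures | investigator assessment | none named |

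Of the three protocol-defined groups, only ketoacidosis rests on the flag alone. Renal and hepatic events also have laboratory summaries that need no flag (creatinine doubling; ALT/AST with bilirubin; SAP 7.8.2).

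**2. Is there another trial-level route?** Adjudication does not provide one in this trial's analysis, because SAP 7.8.1.12 defers it. DKA adjudication was itself added only in Amendment 3 (Protocol 11.3). The printed date of Amendment 3, 14 April 2015, precedes that of Amendment 2, but its log cites an Investigator's Brochure of 11 February 2016, so the printed year looks like a clerical error. Nothing here depends on it.

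**3. Had recruitment started before Amendment 2?** Yes. The Amendment 2 rationale for the new sample size cites low recruitment rates already occurring. SAP Table 6.2: 1 carries criterion numbers specific to protocol versions 1 and 2. The current protocol is version 5.0 after four amendments, so versions 1 and 2 are the original and Amendment 1, both before the ketoacidosis AESI.

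**4. Timing.** The synopsis gives "Protocol date: 15Apr2014".

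- 15 April 2014 to 12 August 2015: 365 + 119 = 484 days.
- Amendment 1 (16 December 2014) to Amendment 2: 239 days.

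These are intervals between document dates. The change also needed IRB and authority approval before use, so it took effect at sites no earlier than the amendment date.

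**5. Exposure.** The share of patient time without the AESI definition would be (patient time before the amendment took effect) / (total patient time). The documents give neither term, so the share cannot be calculated.

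**The case against.** The strongest reply is that no event is lost. Protocol 5.2.2.2 requires all AEs to be collected from consent onwards. They are coded with the MedDRA version current at database lock and tabulated by SOC and PT, with separate tables for SAEs, discontinuations and drug-related AEs (SAP 7.8.1.3). A ketoacidosis that led to hospital admission would be in the SAE table. This stands, and it limits the point to the AESI summary.

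Second, the CRF is not in the documents. Older AEs may have been flagged after the amendment, and the quality review and blinded report planning meetings mentioned in SAP 7.8.1.2 could have prompted this. It cannot be excluded. It is also not described, so the point holds only on the condition that no such flagging took place.

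Third, ketoacidosis is not the only AESI without a term search: the last row of the table above has none either. Project-level adjudication is also not peculiar to DKA, since hepatic and cancer adjudication are handled the same way. Both observations are correct. They do not remove the difference from the other two protocol-defined groups, or the late introduction.

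Fourth, parts of the SAP are blacked out, including the entries for Section 9 in the table of contents. A search list could sit there, so the statement covers the visible text only.

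**Conclusion.** The point holds as a modest one. The ketoacidosis AESI was introduced during recruitment, is identified only by an investigator flag, and has no term search in the visible SAP text. If older AEs were not flagged retrospectively, an event before the amendment could be missing from the AESI summary while the denominator includes all treated patients. The general SOC/PT table and, where it applies, the SAE table would still show it.

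A reader might infer three stronger things, none of which the documents support:

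- **A size taken from the calendar.** For example, 484 of the 1,074 days from the protocol date to the revised SAP (24 March 2017) is 45%, and 239 of the 829 days from Amendment 1 is 29%. These are shares of the time between documents, not of patient time. Low recruitment before Amendment 2, and the added sites and wider eligibility from Amendment 2 onwards, suggest that exposure fell more in the later period.
- **A rate that is certainly biased downwards.** This would need an unflagged event and no retrospective flagging. The same rule applies to both randomised arms, so the text gives no ground for claiming a bias between arms.
- **A conclusion that one missed event would overturn.** Safety analyses are descriptive without hypothesis testing (Protocol 7.3.3), and no decision rule for DKA exists.

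**What to change.** In SAP 7.8.1.5, add an AE frequency table for metabolic acidosis, ketoacidosis and DKA on the treated set. Base it on a MedDRA term list fixed in advance and apply it regardless of the protocol version under which the patient was treated. Show it beside the flag-based count so that any difference is visible.

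The cost is a short addition to the SAP and one more descriptive table on AEs already collected and coded. The drawback is that a term search may pick up some non-specific acidosis terms, which is a further reason to show both counts. No clinical procedure changes.
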